4. SELECTION AND WITHDRAWAL OF SUBJECTS

4.1 Inclusion Criteria

Subjects must satisfy the following criteria before entering the study:

1. Subject is male or female, ≥ 18 years of age.
2. Subject either has medically-confirmed diagnosis of chronic constipation (per Rome III; [Appendix 1](#)), or meets the diagnosis as confirmed using the Rome III constipation module questionnaire ([Appendix 2](#)) during the Screening period.
3. Subject is able to comprehend and willing to sign an ICD approved by the IRB after explanation of the nature and objectives of the study and prior to the conduct of any study specific procedure.
4. If subject is taking concomitant medication (prescribed or over-the-counter) that affects gastrointestinal motility, he/she must discontinue use at the time of the Screening Visit (Visit 1) through the Follow-up Visit (Visit 4); these medications include:
 - a. Cholinesterase inhibitors; anti-spasmodic, anti-diarrheal, anti-constipation, or prokinetic agents; laxative agents (e.g., PEG 3350), including homeopathic remedies;
 - b. Tricyclic antidepressants; and/or
 - c. Any medication, at the discretion of the Investigator, known to relieve or cause constipation or constipation-related symptoms, and which the Investigator, based on the medical history of the subject, suspects to be a contributing factor to the patient's chronic constipation, or may otherwise confound the evaluation of treatment response.

Exceptions: Treatment with anticholinergic agents, SSRIs, SNRIs, or MAO inhibitors is allowed if a stable dose has been used for at least 30 days prior to the Screening Visit and not likely to change during the study.

5. If subject is taking a fiber supplement or a concomitant medication for the indication of lowering blood pressure, usage must have been at a stable dose and schedule for at least 30 days prior to the Screening Visit and not likely to change during the study.
6. Subject daily diary is at least 70% compliant for evening/end-of-day assessments during the Screening period.
7. Subject daily diary indicates an average of less than 3 spontaneous bowel movements (SBMs) per week during the 14 days prior to randomization.
8. Subject daily diary indicates one or more of the following for at least 25% of SBMs during the 14 days prior to randomization:
 - Bristol Stool Scale Type 1 or 2;
 - Moderate to very severe straining associated with SBMs; and/or
 - Sensation of incomplete evacuation.

Note: For subjects with no reported SBMs during the Screening Period, it is not necessary to meet criteria for bowel movement characteristics, i.e., moderate to severe straining and straining at defecation.

4.2 Exclusion Criteria

Subjects who meet any of the following criteria will be excluded from participating in the study:

1. Subject has known or suspected anatomic or organic disorders of the large or small bowel; e.g.:
 - a. Associated with a mechanical bowel obstruction (e.g., tumor, hernia, obstructive polyps), or pseudo-obstruction;
 - b. Associated with large or small bowel disorder such as ulcerative colitis or Crohn's disease.
2. Subject is a candidate for, or has undergone abdominal surgery for which an impact on GI transit/motility or defecation cannot be excluded such as bowel resection, colectomy, and gastric bypass surgery (exceptions: appendectomy, cholecystectomy, benign polypectomy and inguinal hernia).
3. Subject has any gastrointestinal (GI) condition, other than constipation, affecting GI motility or defecation.
4. Subject reports weight loss, anemia, and/or rectal bleeding AND has no documentation of the results of either a flexible sigmoidoscopy or colonoscopy performed during the 6 months prior to dosing since the report of that condition or has documented evidence suggestive of a non GI-related etiology as a cause of these symptoms.
5. Subject has a history of loss of consciousness and/or syncope; has been diagnosed with, or has current evidence of, hypotension (i.e., systolic pressure <90 mmHg and/or diastolic pressure <60 mmHg) based upon orthostatic vital sign measurements taken at the time of screening; and/or has any other medical/surgical condition that might interfere with the absorption, distribution, metabolism, or excretion of the study medication.
6. Subject has taken a systemic antibiotic within 30 days prior to screening or is scheduled to take this at any time during the study.
7. Subject has an uncontrolled cardiovascular, liver or lung disease, neurologic or psychiatric disorder, or other systemic disease, which the Investigator feels is clinically significant and would limit the subject's ability to participate in the trial.
8. Subject is unable to eat or drink, take oral medications, or to hold down oral medications due to vomiting.
9. Subject has impaired renal function (i.e., serum creatinine concentration > 1.8 mg/dL) as identified at the Screening Visit, or is known to have impaired hepatic function (Child-Pugh B or C).
10. Subject has abnormalities in vital signs, electrocardiogram (ECG), or laboratory test results (hematology, urinalysis, or blood chemistry) that cannot be explained by underlying comorbidity(ies) and which, in the Investigator's opinion, are clinically significant, relevant, and should preclude the subject's participation in the trial.

11. Subject has current evidence of, or has been treated for, cancer within the past 5 years, with the exception of localized basal cell, squamous cell skin cancer, or *in situ* cancer which has been resected.
12. Subject (female of childbearing potential) is currently breastfeeding or plans to breastfeed, has a positive pregnancy test, refuses/unwilling to undergo pregnancy testing, and/or does not agree to use protocol-specified contraceptive for the duration of the study.
13. Subject demonstrates a potential for non-compliance with the study protocol (i.e., dosing schedule, visit schedule, or study procedures).
14. Subject has received an investigational medication within 30 days prior to the Screening Visit (Visit 1), or plans to participate in another clinical trial during the study period.
15. Subject has received AMITIZA, lubiprostone, SPI-0211, or RU-0211 at any time prior to participation in this study.

4.3 Reproductive Potential

All female subjects of childbearing potential will have a serum pregnancy test performed at Screening and a urine pregnancy test at Randomization (Visit 2) and Follow-up. Childbearing potential will be defined as any female subject who has not undergone surgical sterilization within the last 3 months or who is not post-menopausal for at least 1 year.

4.4 Contraception Specifications

Sexually active females and their partners must agree to use adequate contraception during study participation.

The type of contraception being used by the subject shall be recorded in the source document. Adequate contraception is defined as use of any of the following:

- Oral Contraceptives— must have been used for at least 3 months prior to the Screening Visit (Visit 1);
- Intrauterine Device (IUD); or
- Double barrier method.

4.5 Withdrawal of Subjects

A subject is free to withdraw from the study at any time for any reason without prejudice to their future medical care by the physician or at the study site. The Investigator or Sponsor may also withdraw the subject at any time in the interest of subject safety. The primary reason for withdrawal must be recorded in the subject's source documents and on the withdrawal form in the electronic Case Report Form (eCRF).

Subject participation may be terminated prior to completion of the clinical study for any of the following reasons:

- AE;
- Lack of efficacy;

- Subject choice;
- Lost to follow-up;
- Non-compliance with study drug;
- Investigator decision;
- Sponsor request; or
- Any other reason upon agreement between the Investigator and the Sponsor.

Subjects who withdraw from the study early or who are terminated from the study should complete the End-of-Treatment and Follow-up procedures as outlined in [Sections 6.1.3.1 and 6.1.4](#).

Attempts should be made to locate subjects who are lost to follow-up so that as much study information as possible may be obtained. Every effort should be made to retrieve dispensed study medication, electronic diaries, and obtain the general overall status of the subject at the time of withdrawal from the study. The subject's source documents should verify that at least two attempts have been made by telephone to locate the subject and that a final attempt to locate the subject has been made by certified or traceable mail.

4.6 Emergency Unblinding

As a double-blinded, placebo-controlled study, both the subjects and Investigators are blinded to the study treatment assignment. In addition, clinical research personnel, laboratory personnel, and others are blinded to the treatment assignment and will remain blinded through the completion of the study.

In the event emergency unblinding of study treatment is necessary, the Investigator shall utilize the interactive response technology (IRT) system to obtain subject dose details. The individual subject dose details should be revealed only in case of an emergency where the further treatment of the subject is dependent on knowing the study medication he or she has received. The date and time of breaking the blind as well as the reason must be recorded on the subject study medication record. The subject will be automatically discontinued from the study in the event emergency unblinding of study treatment takes place. If a blind is broken due to an adverse event, a corresponding adverse event entry must be completed in the eCRF.

It is strongly encouraged that unblinding only be completed after consultation with the study medical monitor, provided this does not compromise subject safety. If unblinding should occur (either by accident or for a medical emergency), the Investigator must promptly and immediately notify the study medical monitor, and IRB/IEC, and document the circumstances surrounding this action in a memorandum to the study file.

4.7 Stopping Rules

4.7.1 Individual Stopping Criteria

The following stopping criteria should be applied for individual subjects who experience one or more of the following spontaneously-reported adverse events:

- Loss of consciousness, hypotension (blood pressure <90 mmHg systolic and/or <60 mmHg diastolic, or a decrease of ≥20 mmHg from pre-dose), ischemic colitis, and severe hypersensitivity reactions/anaphylaxis should result in immediate discontinuation.
- Severe, treatment-related cases of diarrhea, tachycardia, chest discomfort/chest pain, and dyspnea should result in discontinuation.

4.7.2 Overall Study Stopping Criteria

The study will be stopped if at least 2 subjects experience the same treatment-related, life-threatening event.

Draft

5. STUDY AND CONCOMITANT TREATMENTS

5.1 Study Medication Formulation

Lubiprostone drug substance is white, odorless crystals or crystalline powder and is very soluble in ether and ethanol, and practically insoluble in hexane and water. Lubiprostone is available for oral administration as a multi-particulate Sprinkle formulation, or a Capsule formulation in this study. Matching placebo will be supplied for the study.

The Sprinkle formulation consists of micro-beads of multi-layer coating. The core of the beads is inactive (cellulose based material) and the drug substance is carried in one of the polymer coatings. The coated beads are filled in easy-to-open and easy-to-handle oversized hard capsules. The capsule formulation consists of a soft-gelatin capsule that is filled with lubiprostone dissolved in medium chain fatty acid triglycerides (MCT) solution.

5.2 Packaging

The lubiprostone formulations and the corresponding matching placebo will be manufactured and packaged by an independent company. An independent packaging company, not involved in the conduct or monitoring of the study, will label and distribute study medication. Study medication will be provided to the site for distribution by authorized personnel to subjects according to the randomization code.

5.3 Labelling

All study medication product will be labeled with a minimum of the following information:

- Protocol Number;
- Kit Number (if applicable);
- Dosage form (including product name and quantity in pack);
- Manufacturing information;
- Directions for use, storage conditions, expiry date (if applicable), batch number;
- The statements 'For clinical trial use only', and/or 'CAUTION: New Drug - Limited by Federal (United States) Law to Investigational Use', as applicable;
- The Sponsor's name and address;
- Subject Number (To be written by the site);
- Dispense Date (To be written by the site).

5.4 Storage and Handling

The Investigator has overall responsibility for ensuring that study medication is stored in a safe, limited-access location under the specified appropriate storage conditions. The study medication will be stored at controlled room temperature of 20 °C (68 °F) to 25 °C (77 °F); excursions between 15°C and 30°C (59°C to 86°F) are allowed. Limited responsibility may be delegated to the pharmacy or member of the study team, but this delegation must be documented. Study medication will be distributed by the pharmacy or nominated member of the study team. Temperature monitoring is required at the storage location to ensure that the investigational product is maintained within an established temperature range. The Investigator

is responsible for ensuring that the temperature is monitored throughout the total duration of the trial and that records are maintained.

No study medication stock or returned inventory may be removed from the investigational site without prior knowledge and consent by the Sponsor. All returned and unused study medication shall be returned or destroyed as instructed by the Sponsor.

The Sponsor will be permitted upon request to inspect the supplies storage and distribution procedures and records provided that the blind of the study is not compromised.

5.5 Supply and Dosing

Treatments will be blinded and double-dummy, whereby subjects will be randomized to either lubiprostone sprinkle, lubiprostone capsule, or matching placebo doses BID. Each treatment day should consist of two (2) doses of study medication, one dose in the morning and one dose in the evening with meals. The Sprinkle formulation is supplied in an easy-to-open hard capsule and will be sprinkled onto a teaspoon of applesauce for oral administration, followed by intake of 240 mL of water. The Capsule formulation will also be taken with 240 mL of water.

All doses should be taken at least 5 hours apart. The subject should record the actual time the dose was taken in the electronic diary. If taken late, the site personnel should record the actual time the dose was taken in the subject records. If the dose was missed entirely, the subject should indicate the omission in the electronic diary as instructed. The study medication will be handled by authorized personnel and dispensed under the supervision of the Investigator or designated study personnel.

Subjects should return the used bottles of study medication at Visit 3 for collection by site for drug accountability. If the study medication is not returned, all bottles of unused study medication should be returned to the site at the subsequent office visit (Visit 4). The last dose of study medication in this study will be taken the evening before Visit 3.

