ITT	Intention-to-Treat
LDH	Lactose Dehydrogenase
MAO	Monoamine Oxidase
MCH	Mean Corpuscular Haemoglobin
MCHC	Mean Corpuscular Haemoglobin Concentration
MCV	Mean Corpuscular Volume
MedDRA	Medical Dictionary for Regulatory Activities
MHRA	Medicines and Healthcare products Regulatory Agency (UK)
mL	Milliliters
NCS	Not Clinically Significant
NDA	New Drug Application
OC	Observed Case
OIC	Opioid-induced Constipation
OTC	Over-the-Counter
PP	Per Protocol
QD	Once Daily
RBC	Red Blood Cells
SAE	Serious Adverse Event
SAP	Statistical Analysis Plan
SBM	Spontaneous Bowel Movement
SNRI	Serotonin–Norepinephrine Reuptake Inhibitor
SOC	System Organ Class
SSRI	Serotonin-Specific Reuptake Inhibitor
WBC	White Blood Cell
WHO	World Health Organization

PROTOCOL SYNOPSIS

A Randomized, Placebo-controlled, Double-blinded, Multicenter Study of the Bioequivalence of Sprinkle and Capsule Formulations of Lubiprostone, as Compared to Placebo, in Adult Subjects with Chronic Idiopathic Constipation
		
Study Phase:	Phase 3	
Short Title:	Evaluation of the bioequivalence of sprinkle and capsule formulations of lubiprostone, as compared to placebo, in adults with chronic idiopathic constipation (CIC)	
Objectives, Study Medication and Dose Regimen:	
To evaluate the bioequivalence of sprinkle and capsule formulations of lubiprostone, as compared to placebo, when administered orally (at 24 mcg twice daily [BID]) in subjects with CIC.
 
Dose: 0 or 24 mcg BID (48 mcg/day)
 
All subjects will take study medication BID from Day 1 through the evening of Day 7 and will return to the clinic on the morning of Day 8 for their End-of-Treatment (EOT) visit.
	
Assumed No. of Sites:	Approximately 70 (United States)	
Est. No. Enrolled Subjects:	
Approximately 522; 1:1:1 randomization (placebo: 24 mcg Sprinkle: 24 mcg Capsule; 174 subjects per arm); stratified by baseline spontaneous bowel movement (SBM) frequency rate (<1.5 or ≥1.5) and site.
	
Est. No. Screened Subjects:	1,044	
Duration of Participation:	Approximately 4 weeks (including screening and follow-up)	
Duration of Treatment:	7-day treatment	
Study Schedule:	
Visit 1: Screening (Clinic Visit); Note: All subjects will complete daily diaries to record bowel habits, which will be used to confirm CIC eligibility
 
Visit 2: Randomization & Treatment Period
 
Visit 3: End-of- Treatment (All subjects)
 
Visit 4: Follow-up
	Day -14 (-3 day window)

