⁹ Observe the subject as he/she administers the first dose of study medication while in the clinic at Visit 2. One bottle of study medication and applesauce will be distributed at this visit. For all subjects, the last dose of treatment will be administered the evening before Visit 3;

¹⁰ Subjects should return the bottle of study medication to the site at Visit 3 for drug accountability. If the study medication is not returned, the bottle should be returned to the site at the subsequent office visit (Visit 4);

¹¹ A follow-up clinic visit will occur approximately 7 days after the last clinic visit to review any on-going or evaluate newly occurring adverse events (AEs), to record any changes in concomitant medications, to assess the subject's condition via physical examination, and to obtain laboratory samples. This will conclude the subject's involvement in the study.

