3. STUDY DESIGN

This is a phase 3, multicenter, double-blinded, randomized, placebo-controlled study evaluating the bioequivalence of sprinkle and capsule formulations of lubiprostone, as compared to placebo, when administered orally in subjects with CIC. Approximately 522 subjects will be randomized to study treatment in a 1:1:1 ratio to receive either lubiprostone Sprinkle 24 mcg BID, Capsule 24 mcg BID, or matching placebo BID from the morning of Day 1 through the evening of Day 7 before returning to the clinic on the morning of Day 8. The Sprinkle formulation of lubiprostone (24 mcg) is supplied in an easy-to-open and easy-to-handle oversized hard capsule and will be sprinkled onto a teaspoon of applesauce for oral administration, followed by intake of 240 mL of water. The Capsule formulation (24 mcg) is supplied as soft-gelatin capsules and will be taken with 240 mL of water. Doses should be taken with meals.

Enrollment at approximately 70 sites within the United States is anticipated. Duration of subject participation is approximately 4 weeks from the beginning of the Screening period until the Follow-up visit. A schematic representation of the study design is provided below in Figure 1.

[figure not shown]

Figure 1: Study Design Flow Chart

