5.5.1 Randomization and Blinding

There will be approximately 522 subjects randomized 1:1:1 to the following treatment arms:

- Treatment A: Lubiprostone sprinkle plus placebo capsule; taken BID for 7 days
- Treatment B: Lubiprostone capsule plus placebo sprinkle; taken BID for 7 days
- Treatment C: Placebo capsule plus placebo sprinkle; taken BID for 7 days

An independent third party will generate and hold the randomization code throughout the conduct of the study. Each investigational site will randomize subjects to treatment groups using the Interactive Response Technology (IRT) system with balancing factors for baseline SBM frequency rate (<1.5 or \geq 1.5) and site.

Most study personnel will remain blinded until the clinical database has been locked. To allow for the execution of clinical trial-related services, the following individuals will be unblinded during the study:

- Sponsor Quality Assurance representative
- External IRT vendor
- Sponsor Pharmacovigilance representative
- Sponsor Regulatory representative
- External clinical supply distribution vendor
- Sponsor Drug Supply Management representative

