6.1.2.2 Randomization Visit – Visit 2 (Day 1)

The treatment period will begin at randomization when the first dose of study medication is administered on the morning of Study Day 1 and will continue with BID dosing thereafter through administration of the last dose on the evening of Day 7.

On Day 1, the following procedures will be performed:

- Review the diary record to confirm that the subject meets the necessary inclusion criteria;
- Update medical history. Any new medical information should be added to the subject's baseline history (AEs will be captured on the AE page);
- Collect blood and urine samples for laboratory analysis;
- Review and record any new AEs and follow-up on any ongoing AEs;
- Measure weight;

- Update Concomitant Therapy – Concomitant medications (prescribed and OTC) used since the Screening Visit will be reviewed;
- Measure vital signs (body temperature, respiration rate, and orthostatic blood pressure and heart rate [i.e., first measurement after 5 minutes in supine position, followed by a second measurement after 5 minutes in standing position]) at 0 hour (pre-dose) and at 1 hour post-dose. If abnormalities in blood pressure (i.e., systolic pressure <90 mmHg and/or diastolic pressure <60 mmHg, or a decrease in orthostatic systolic and/or diastolic pressure [from supine to standing] of ≥20 mmHg) are observed at 1-hour post-dose, a repeat measurement of orthostatic blood pressure and heart rate must be taken at 2 hours post-dose. If abnormalities persist at 2 hours post-dose, subject should be discontinued immediately, and an AE of hypotension should be recorded;
- Dispense study medication, providing dosing instructions (see [Section 5.5](#)) and remind the subject to bring the bottle back at the next visit;
- Observe the subject as he/she administers the first dose of study medication while in the clinic and record time of study medication administration in the electronic diary.
- If the subject is randomized, the diary must be switched to “treatment period” mode and the subject must continue completing the diary each day during the treatment period. Diary data will be automatically transmitted from the device each night. The diary will record information for the entire period prior to the next scheduled office visit;
- Remind the subject that rescue medication is prohibited during the treatment period; and
- Schedule the next clinic visit (Visit 3).

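### Section 5.5 and schedule footnote 9 tie the last dose to the date of Visit 3, which may be Day 8 to Day 10, while the rest of the protocol ends dosing on the evening of Day 7

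*Combined protocol and SAP*

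**What the plan says.** Two places define the end of dosing by the visit. The last sentence of Section 5.5 reads "The last dose of study medication in this study will be taken the evening before Visit 3", and footnote 9 of the Schedule of Evaluations reads "For all subjects, the last dose of treatment will be administered the evening before Visit 3". The schedule, Section 3.1 and Section 6.1.3.1 all allow Visit 3 on Day 8 with +2 days, that is, Day 8 to Day 10.

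Four places define the end of dosing by the calendar:

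- Synopsis: "All subjects will take study medication BID from Day 1 through the evening of Day 7".
- Section 3: "from the morning of Day 1 through the evening of Day 7".
- Section 6.1.2.2: "through administration of the last dose on the evening of Day 7".
- Section 5.5.1, for Treatment A and likewise for the other two arms: "Lubiprostone sprinkle plus placebo capsule; taken BID for 7 days". This gives a duration and not a day, but with a morning start on Day 1 it comes to the evening of Day 7.

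Section 6.1.3 ends treatment on the evening before the clinic visit and names that visit as Day 8, so it agrees with the Day 7 rule.

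On supply, footnote 9 says "One bottle of study medication and applesauce will be distributed at this visit". The number of doses in the bottle is not given.

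**The concern.** A site whose subject comes in on Day 9 or Day 10 cannot follow both rules, and no sentence says which one takes precedence. Section 5.5 is operative text: Section 6.1.2.2 refers sites to it for the dosing instructions they give to subjects. A subject told to keep dosing until the evening before the visit could exceed the planned 7 days.

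Exposure and safety data are what is at stake. Sections 7 and 8.6.2 count an adverse event as treatment-emergent up to 7 days after the last dose day, so a later last dose moves the end of that window. Section 6.1.1 dates all visits from the first dose, so Visit 4 does not automatically move with it. The compliance measure would not reveal the extra doses either, because Section 8.4.1 takes as its denominator the days actually exposed times 2, not the planned 14 doses.

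**Working it through.** Inputs:

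- 2 doses per day (Section 5.5).
- Visit 3 on Day 8, 9 or 10 (Sections 3.1 and 6.1.3.1).
- Visit 4 on Day 15 to Day 18 (Section 3.1).
- Treatment-emergent window ending at the last dose day plus 7 (Section 7).
- Expected doses equal to exposure days × 2 (Section 8.4.1).
- Per Protocol dosing compliance between 75% and 125% (Section 8.2).

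The plan's own figure: Day 1 to the evening of Day 7 is 7 days, and 7 × 2 = 14 doses. The window ends on Day 7 + 7 = Day 14.

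Under the rule in Section 5.5 and footnote 9, with V3 the day of Visit 3:

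- last dose day = V3 − 1
- doses = 2 × (V3 − 1)
- window end = (V3 − 1) + 7

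| Visit 3 | Last dose | Doses | Relative to 14 | Compliance under 8.4.1 | Window ends | Window end minus a Day 15 Visit 4 |
|---|---|---|---|---|---|---|
| Day 8 | Day 7 | 14 | 100% | 14/14 = 100% | Day 14 | −1 day |
| Day 9 | Day 8 | 16 | 16/14 = 114.3% | 16/16 = 100% | Day 15 | 0 days |
| Day 10 | Day 9 | 18 | 18/14 = 128.6% | 18/18 = 100% | Day 16 | +1 day |

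The visit-based rule gives the planned 14 doses only in the first row.

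Compliance: a subject who takes all 18 doses shows 100% and passes the Per Protocol filter. Measured against the planned 14 doses, the same subject would be at 128.6%, above the 125% limit.

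Adverse event window: it outlasts a Day 15 Visit 4 only when Visit 3 is on Day 10, and then by one day. Footnote 11 gives another spacing: "A follow-up clinic visit will occur approximately 7 days after the last clinic visit". With Visit 4 at V3 + 7, the visit falls on Day 15, 16 or 17, always one day after the window ends on Day 14, 15 or 16, and no gap arises.

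Supply: doses taken cannot exceed the bottle's content, which is an assumption here. With 14 doses in the bottle, no extra dosing is possible. With 16, the maximum is 16. With 18 or more, it is 18.

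With the last dose fixed on the evening of Day 7, every completer has 14 planned doses and a window ending on Day 14, whichever of the three days Visit 3 falls on.

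**The case against.** The best counter-argument is that the intended meaning is already clear. The 7-day duration is stated many times, and Section 6.1.3 shows that the evening before the visit is shorthand for a visit on the nominal Day 8. A site sent to Section 5.5 also finds the 7-day limit in Section 5.5.1. Nor can the visit-based sentence be a literal rule for everyone: Section 3.1 holds Visit 3 for subjects who stop early too, and their last dose need not fall on the evening before it.

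The consequences are also conditional. Extra doses need surplus supply, and the pack label and subject instructions, which might prevent them, are not available to check. The adverse event gap needs literal use of Section 5.5, enough supply, Visit 3 on Day 10 and Visit 4 on exactly Day 15, which is only 5 days after Visit 3 when footnote 11 suggests about 7. Section 7.2 also asks for related serious events to be reported even after the study ends.

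All of this stands as a limit on the weight of the point. It does not remove the conflict: Section 6.1.3 shows what was meant but does not correct the two dosing sentences, and footnote 9 applies its rule expressly to all subjects.

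**Conclusion.** The inconsistency is real, and the two sentences are wrong as written for any Visit 3 on Day 9 or Day 10. The discrepancy is one or two days of dosing, at most 16 or 18 doses against 14. These are upper bounds that assume the bottle holds enough and the site follows Section 5.5 literally; they are not expected effects. The treatment-emergent window could run to Day 16, one day past the earliest permitted Visit 4, in a single corner case. The Week 1 count is unaffected, because the extra doses would come after Day 7. This is a minor point that is worth correcting. Confidence is high on the conflict in the text; whether any subject would in fact be overdosed cannot be determined from the documents.

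**What to change.** In the last sentence of Section 5.5 and in footnote 9, state that the last dose is taken on the evening of Day 7 regardless of the date of Visit 3, and bring the dosing instruction given to subjects into line. Section 6.1.3 needs no change. The treatment-emergent window then closes on Day 14 for every completer, before any permitted Visit 4.

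The cost is a few words in two places plus the subject instruction. There is one small downside: end-of-treatment laboratory tests and vital signs at a Day 9 or Day 10 visit will be taken 2 or 3 days after the last dose. The Day 7 rule elsewhere in the protocol already implies that gap.
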